3.7.1.4 AE summaries

The following adverse event summaries will be produced by treatment group:

- Summary of deaths and adverse events
- Adverse events, irrespective of causality, by primary system organ class, preferred term and maximum grade
- Adverse events with suspected relationship to study treatment by primary system organ class, preferred term and maximum grade
- Most common grade 3-4 adverse events, irrespective of causality, by preferred term and maximum grade (greater than x% in either arm)
- Adverse events, irrespective of causality, by primary system organ class and maximum grade
- Adverse events, irrespective of causality, by preferred term and maximum grade
- Adverse events with suspected relationship to study treatment by preferred term and maximum grade
- Grade 3 or 4 adverse events, irrespective of causality, by primary system organ class, preferred term and maximum grade
- Grade 3 or 4 adverse events with suspected relationship to study treatment by primary system organ class, preferred term and maximum grade
- On treatment deaths by preferred term
- Deaths, by primary system organ class and preferred term
- Serious adverse events, irrespective of causality, by primary system organ class and preferred term and maximum grade
- Serious adverse events with suspected relationship to study treatment, by primary system organ class, preferred term and maximum grade
- Adverse events leading to study drug discontinuation, irrespective of causality, by primary system organ class, preferred term and maximum grade
- Adverse events leading to study drug reductions, irrespective of causality, by primary system organ class, preferred term and maximum grade
- Adverse events leading to study drug interruptions, irrespective of causality, by primary system organ class, preferred term and maximum grade
- Adverse events requiring additional therapy, irrespective of causality, by primary system organ class, preferred term and maximum grade
- On-treatment deaths and SAEs with fatal outcome, by SOC and PT

AEs of interest will also be summarized. See [Section 3.7.1.5](#) for the grouping details.

3.7.1.5 Grouping of adverse events of special interest

An adverse event of special interest is a grouping of adverse events that are of scientific and medical concern specific to ribociclib. These groupings are defined using MedDRA terms, SMQs (standardized MedDRA queries), HLGs (high level group terms), HLTs (high level terms) and PTs (preferred terms). Customized SMQs (Novartis MedDRA queries, NMQ) may also be used. A NMQ is a customized group of search terms which defines a medical concept for which there is no official SMQ available or the available SMQ does not completely fit the need. It may include a combination of single terms and/or an existing SMQ, narrow or broad. For each specified AESI, the number and percentage of patients with at least one event of the AESI occurring during the double-blinded on-treatment period will be summarized.

Summaries of these AESIs will be provided by treatment arm, (specifying grade, SAE, relationship, leading to treatment discontinuation, leading to dose adjustment/interruption, etc.).

A Case Retrieval Sheet (CRS) with the exact composition of the AE groupings is to be used to map reported AEs to the AESI groupings. This file may be updated (i.e., it is a living document) based on review of accumulating trial data, and therefore the groupings are also subject to potential change. The most up-to-date version of the CRS will be used at the time of the analysis.

3.7.1.6 Clinical trial safety disclosure

For the legal requirements of ClinicalTrials.gov and EudraCT, two required tables adverse events which are not serious adverse events with an incidence greater than 5% and serious adverse events and SAE suspected to be related to study treatment will be provided by system organ class and preferred term on the safety set and the cross-over analysis set population.

If for a same patient, several consecutive AEs (irrespective of study treatment causality, seriousness and severity) occurred with the same SOC and PT:

- a single occurrence will be counted if there is ≤ 1 day gap between the end date of the preceding AE and the start date of the consecutive AE
- more than one occurrence will be counted if there is > 1 day gap between the end date of the preceding AE and the start date of the consecutive AE

For occurrence, the presence of at least one SAE / SAE suspected to be related to study treatment / non SAE has to be checked in a block e.g., among AE's in a ≤ 1 day gap block, if at least one SAE is occurring, then one occurrence is calculated for that SAE.

The number of deaths resulting from SAEs suspected to be related to study treatment and SAEs irrespective of study treatment relationship will be provided by SOC and PT.

3.7.2 Laboratory data

On analyzing laboratory data, data from all sources (central and local laboratories) will be combined. The summaries will include all laboratory assessments collected no later than 30 days after the last administration of study treatment or the date of the day prior to the start of open-label ribociclib plus fulvestrant treatment.

Laboratory data will be classified (by biostatistics/statistical programming) into CTC grades according to the NCI Common Terminology Criteria for Adverse Events (CTCAE) v4.03. The calculation of laboratory CTC grades will be based on the observed laboratory values only; clinical assessments will not be taken into account. The criteria to assign CTC grades in this study are given in Appendix 1.

For laboratory tests where grades are not defined by CTCAE, results will be graded by the low/normal/high classifications based on laboratory normal ranges.

The following summaries will be produced for the laboratory data (by laboratory parameter):

- Number and percentage of patients with each CTC grade as their worst post-baseline value (regardless of the baseline status). Each patient will be counted only for the worst grade observed post baseline.
- Shift tables using CTC grades to compare baseline to the worst post-baseline value will be produced for hematology and biochemistry laboratory parameters with CTC grades.
- For laboratory parameters where CTC grades are not defined, shift tables to the worst post-baseline value will be produced using the low/normal/high classifications based on laboratory reference ranges.

Number and percentage of patients meeting categorical liver function test criteria, including ALT, AST and ALT/AST (>3x, 5x, 8x, 10x, 20x ULN), Total Bilirubin (>1x, 2x ULN), ALP (>1.5x, 2x, 3x, 5x, 8x, 10x ULN), combined categories of ALT/AST and total bilirubin (e.g., ALT/AST>3x UNL & total bilirubin > ULN) as well as Hy's Law criteria (ALT or AST > 3 x ULN and TBIL \geq 2 x ULN and ALP < 2 x ULN). For the combined categories, the assessments need not to be concurrent, i.e., patients are counted based on their most extreme value for each parameter (highest in the case of ALT, AST and TBIL; lowest in the case of ALP). Listing of patients with CTC grade 3 or 4 laboratory abnormalities will be produced and those assessments collected later than 30 days after the last double-blinded study treatment date and before the day of the start of cross-over open-label ribociclib plus fulvestrant treatment will be flagged in the listing.

Separate listing will be provided for the cross-over analysis set and those assessments collected later than 30 days after the last cross-over open-label study treatment date will be flagged in the listing.

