  - If no measurable disease is present, then at least one predominantly lytic bone lesion must be present (patients with no measurable disease and only one predominantly lytic bone lesion that has been previously irradiated are eligible if there is documented evidence of disease progression of the bone lesion after irradiation).
6. Patient has advanced (loco regionally recurrent not amenable to curative therapy (e.g. surgery and/or radiotherapy) or metastatic) breast cancer.

Patients may be :

- newly diagnosed advanced/ metastatic breast cancer, treatment naïve
- relapsed with documented evidence of relapse more than 12 months from completion of (neo)adjuvant endocrine therapy with no treatment for advanced/metastatic disease
- relapsed with documented evidence of relapse on or within 12 months from completion of (neo)adjuvant endocrine therapy with no treatment for advanced/metastatic disease
- relapsed with documented evidence of relapse more than 12 months from completion of (neo)adjuvant endocrine therapy and then subsequently progressed with documented evidence of progression after one line of endocrine therapy (with either an antiestrogen or an aromatase inhibitor) for advanced/metastatic disease
- advanced/metastatic breast cancer at diagnosis that progressed with documented evidence of progression after one line of endocrine therapy (with either an antiestrogen or an aromatase inhibitor)

**Note:** Patient who relapsed with documented evidence of relapse on/or within 12 months from completion of (neo)adjuvant endocrine therapy and then subsequently progressed with documented evidence of progression after one line of endocrine therapy (with either an antiestrogen or an aromatase inhibitor) for metastatic/advanced disease will NOT be included in the study.

7. Patient has an Eastern Cooperative Oncology Group (ECOG) performance status 0 or 1
8. [Retired from protocol version 0.0]
  - 8a. Patient has adequate bone marrow and organ function as defined by the following laboratory values (as assessed by central laboratory for eligibility):
    - Absolute neutrophil count  $\geq 1.5 \times 10^9/L$
    - Platelets  $\geq 100 \times 10^9/L$
    - Hemoglobin  $\geq 9.0$  g/dL
    - INR  $\leq 1.5$
    - Serum creatinine  $< 1.5$  mg/dL

- Total bilirubin < ULN except for patients with Gilbert's syndrome who may only be included if the total bilirubin is  $\leq 3.0 \times \text{ULN}$  or direct bilirubin  $\leq 1.5 \times \text{ULN}$ .

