- Aspartate transaminase (AST) <  $2.5 \times \text{ULN}$ , except for patients with liver metastasis, who are only included if the AST is <  $5 \times \text{ULN}$
- Alanine transaminase (ALT) <  $2.5 \times \text{ULN}$ , except for patients with liver metastasis, who are only included if the ALT is <  $5 \times \text{ULN}$
- Patient must have the following laboratory values within normal limits or corrected to within normal limits with supplements before the first dose of study medication:
  - Sodium
  - Potassium
  - Magnesium
  - Total Calcium (corrected for serum albumin)

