### 6.5.1.2.1 Additional follow-up for hepatic toxicities

Increase in transaminases combined with total bilirubin (TBIL) increase may be indicative of drug-induced liver injury (DILI), and should be considered as clinically important events. The threshold for potential DILI may depend on the patient's baseline AST/ALT and TBIL value; patients meeting any of the following criteria will require further follow-up as outlined below:

- For patients with normal ALT and AST and TBIL value at baseline: AST or ALT > 3.0 x ULN combined with TBIL > 2.0 x ULN
- For patients with elevated AST or ALT or TBIL value at baseline: [AST or ALT > 2 x baseline AND > 3.0 x ULN] OR [AST or ALT > 8.0 x ULN], whichever is lower, combined with [TBIL > 2 x baseline AND > 2.0 x ULN]

Medical review needs to ensure that liver test elevations are not caused by cholestasis, defined as: ALP elevation > 2.0 x ULN with R value < 2 in patients without bone metastasis, or elevation of ALP liver fraction in patients with bone metastasis.

[figure not shown]
Note: The R value is calculated by dividing the ALT by the ALP, using multiples of the ULN for both values. It denotes the relative pattern of ALT and/or ALP elevation is due to cholestatic or hepatocellular liver injury or mixed type injury.

In the absence of cholestasis, these patients must be immediately discontinued from study drug treatment, and repeat LFT testing as soon as possible, preferably within 48 hours from the awareness of the abnormal results. The evaluation should include laboratory tests, detailed history, physical assessment and the possibility of liver metastasis or new liver lesions, obstructions/compressions, etc.

Hepatic toxicity monitoring includes the following LFTs: albumin, ALT, AST, total bilirubin, direct and indirect bilirubin, alkaline phosphatase (fractionated if alkaline phosphatase is grade 2 or higher), creatine kinase, prothrombin time (PT)/INR and GGT. For patients with Gilbert Syndrome: total and direct bilirubin must be monitored, intensified monitoring applies to changes in direct bilirubin only.

Close observation is recommended in case of AST, ALT, and/or bilirubin increase requiring dose interruption, which involves:

- Repeating liver enzyme and serum bilirubin tests **two or three times weekly**. After dose resumption repeat liver enzyme and bilirubin tests twice weekly during the first 2 weeks,

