3.7 Safety evaluation

The assessment of safety will be based mainly on the frequency of adverse events and on the number of laboratory/ECG values that fall outside of pre-determined ranges. Other safety data (e.g., vital signs and special tests) will be considered as appropriate.

All safety outputs will use the safety set. The safety summary tables will include ‘double-blinded on-treatment’ events/assessments, i.e., those collected on or after the first date of study treatment and collected no later than 30 days after the date of last study treatment administration or the date of the day prior to the start of cross-over open-label ribociclib plus fulvestrant treatment. The AEs started before the first dose but worsening during the treatment period are also considered as ‘on-treatment’ events.

Key safety analyses that include data from the cross-over on-treatment period will also be performed on the cross-over analysis set. See Section 2.1.8 for more details on the definition of ‘on-treatment’ event during the cross-over on-treatment period.

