3.9.2 Laboratory data

On analyzing laboratory data, data from all sources (central and local laboratories) will be combined. The summaries will include all laboratory assessments collected no later than 30 days after the last administration of study treatment. All laboratory assessments will be listed and those collected later than 30 days after the last treatment date will be flagged in the listings.

Laboratory data will be classified (by biostatistics/statistical programming) into CTC grades according to the NCI Common Terminology Criteria for Adverse Events (CTCAE) v4.03. The calculation of laboratory CTC grades will be based on the observed laboratory values only; clinical assessments will not be taken into account. The criteria to assign CTC grades in this study are given in Appendix 1.

For laboratory tests where grades are not defined by CTCAE, results will be graded by the low/normal/high classifications based on laboratory normal ranges.

The following summaries will be produced for the laboratory data (by laboratory parameter):

- Box plots of laboratory values by scheduled time point and treatment arm.

- Number and percentage of patients with each CTC grade as their worst post-baseline value (regardless of the baseline status). Each patient will be counted only for the worst grade observed post baseline.
- Shift tables using CTC grades to compare baseline to the worst post-baseline value will be produced for hematology and biochemistry laboratory parameters with CTC grades.
- For laboratory parameters where CTC grades are not defined, shift tables to the worst post-baseline value will be produced using the low/normal/high classifications based on laboratory reference ranges.

Number and percentage of patients meeting categorical liver function test criteria, including ALT, AST and ALT/AST (>3x, 5x, 8x, 10x, 20x ULN), Total Bilirubin (>1x, 2x ULN), ALP (>1.5x, 2x, 3x, 5x, 8x, 10x ULN), combined categories of ALT/AST and total bilirubin (e.g., ALT/AST>3x UNL & total bilirubin > ULN) as well as Hy's Law criteria (ALT or AST > 3 x ULN and TBIL \geq 2 x ULN and ALP < 2 x ULN). For the combined categories, the assessments need not to be concurrent, i.e. patients are counted based on their most extreme value for each parameter (highest in the case of ALT, AST and TBIL; lowest in the case of ALP). The following listings will be produced for the laboratory data:

- Listing of patients with CTC grade 3 or 4 laboratory abnormalities;

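### The SAP's Hy's Law count combines liver values from different visits without regard to baseline, so it can both over-count and under-count against the protocol's potential liver-injury definition

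*SAP*

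**What the plan says.** SAP 3.7.2 sets the criterion as "ALT or AST > 3 x ULN and TBIL" at least 2 x ULN, with ALP below 2 x ULN. Its timing rule reads: "For the combined categories, the assessments need not to be concurrent, i.e., patients are counted based on their most extreme value for each parameter". It then fixes which value of each test is used: "highest in the case of ALT, AST and TBIL; lowest in the case of ALP". No term refers to baseline. SAP 3.7 defines the window as assessments from treatment start ("those collected on or after the first date of study treatment") until 30 days after the last dose or the day before cross-over treatment starts. SAP 3.9.2, written for the primary PFS analysis, repeats the timing rule: "the assessments need not to be concurrent, i.e. patients are counted based on their most extreme value for each parameter".

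The protocol handles the same concept in Table 6-5 and Section 6.5.1.2.1. Table 6-5 groups the transaminase rise with concurrent bilirubin. Section 6.5.1.2.1 states: "The threshold for potential DILI may depend on the patient's baseline AST/ALT and TBIL value". With normal baseline values, the limits are AST or ALT above 3 x ULN combined with bilirubin above 2 x ULN. If any of the three is elevated at baseline, the transaminase limit is more than 2 x baseline and more than 3 x ULN, or more than 8 x ULN. Bilirubin must then exceed both 2 x baseline and 2 x ULN. Cholestasis is excluded by ALP with the R value or, with bone metastases, by the ALP liver fraction.

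Entry criterion 8a allows abnormal liver values in two groups. ALT must be below 2.5 x ULN "except for patients with liver metastasis, who are only included if the ALT is" below 5 x ULN, and AST is treated alike. Total bilirubin must be below ULN "except for patients with Gilbert's syndrome who may only be included if the total bilirubin is" at most 3.0 x ULN, or direct bilirubin at most 1.5 x ULN.

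**The concern.** Hy's Law normally describes one hepatocellular event: transaminases and bilirubin raised together, without cholestasis to explain it. The SAP builds its count from three extremes that may lie many months apart. The lowest ALP on treatment says nothing about cholestasis when ALT and bilirubin were high. A bilirubin that was already raised at entry satisfies its part of the criterion without any change on treatment.

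Amendment 1 was written partly because of hepatic toxicity, and laboratory abnormalities belong to a secondary endpoint. Each Hy's Law case is examined individually, so a few misclassified patients can alter how the table is read. Unrelated pairs also have more opportunity to arise with longer treatment. Treatment continues until progression and PFS favoured ribociclib, so longer exposure in that arm is a reasonable expectation, although the documents do not report it.

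**Working it through.** The plan states no Hy's Law count or rate, so there is no figure to reproduce. The check applies each rule as written to constructed patients.

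**Rules applied**

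- SAP: max(ALT or AST) > 3, max(bilirubin) >= 2 and min(ALP) < 2, all in multiples of ULN, over all on-treatment samples.
- Same sample only: the SAP limits, all met in one sample.
- Protocol: the 6.5.1.2.1 limits met at one visit, using the baseline-dependent version when baseline is abnormal. An event is excluded as cholestatic if ALP > 2 with R < 2, or if the ALP liver fraction is elevated in patients with bone metastases.

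| Profile (x ULN) | SAP | Same sample only | Protocol |
|---|---|---|---|
| A. Normal baseline; ALT 6 early, bilirubin 2.5 much later | yes | no | no |
| B. ALT 4, bilirubin 3, ALP 5 at one visit; ALP 0.9 at another | yes | no | no |
| C. Gilbert's plus liver metastases; ALT 4, bilirubin 2.4, unchanged from entry | yes | yes | no |
| D. Liver metastases only; ALT 4, bilirubin 0.9, unchanged | no | no | no |
| E. Gilbert's only; ALT 2.4, bilirubin 2.4, unchanged | no | no | no |
| F. Gilbert's; bilirubin 2.4 unchanged, ALT 0.8 rising to 3.5 | yes | yes | no |
| G. Bone metastases, total ALP 3 throughout, liver fraction normal; ALT 6, bilirubin 3 at one visit | no | no | yes |
| H. ALT 10, bilirubin 3, ALP 1 at one visit | yes | yes | yes |

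- In B, R = 4/5 = 0.8 with ALP above 2, so the protocol treats the event as cholestatic. The SAP uses the ALP of 0.9 from the other visit.
- In F, ALT 3.5 exceeds 2 x 0.8 = 1.6 and exceeds 3, but bilirubin 2.4 does not exceed 2 x 2.4 = 4.8.
- In G, the lowest ALP is 3, so the SAP drops a patient whom the protocol would count.
- Same-sample pairing alone removes A and B. Removing C and F also needs the baseline term. G is recovered only with the protocol's handling of cholestasis.

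**Visibility.** SAP Appendix 1 grades ALT or AST of >3.0 to 5.0 x ULN and bilirubin of >1.5 to 3.0 x ULN as grade 2. A patient with ALT 4 and bilirubin 2.5 is therefore in the count but need not appear in the grade 3 or 4 listing, which is the laboratory listing that SAP 3.7.2 specifies for the main safety analysis. The listing of all laboratory values in SAP 3.9.2 is not repeated there.

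**Size, under assumptions only.** The rates below are assumptions, not figures from the documents.

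- Chance pairing: assume 5-15% ever have ALT or AST > 3 x ULN and 1-5% ever have bilirubin >= 2 x ULN, independently. In the 727 randomized patients the expected number is 727 x 0.05 x 0.01 = 0.36 to 727 x 0.15 x 0.05 = 5.45, before the ALP condition. In the ribociclib arm (727 x 2/3 = 484.7) it is 0.24 to 3.6.
- Both limits met on entry values (profile C): assume liver metastases in 20-40%, Gilbert's in 3-10%, ALT > 3 x ULN in 2-10% of the former and bilirubin >= 2 x ULN in 5-30% of the latter. The result is 727 x 0.20 x 0.03 x 0.02 x 0.05 = 0.004 to 727 x 0.40 x 0.10 x 0.10 x 0.30 = 0.87 patients.

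**The case against.** The most-extreme-value rule is deliberate. Both analysis plans state it openly, and the primary SAP's change log says that the liver-function analysis was aligned with another ribociclib submission. As a screen it has the merit of catching patients whose ALT and bilirubin peak on different visits. The protocol definition serves case management, and confirmed cases are reported separately as serious adverse events. Hepatobiliary toxicity is also an adverse event of special interest, and shift tables show baseline grades. All of this stands. It makes the rule defensible as a screen, but it does not supply a concurrent count next to a row labelled Hy's Law.

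A full match to the protocol is also not available from routine data. The ALP liver fraction is not in the Table 7-4 panel. Section 6.5.1.2.1 asks for fractionation only from ALP grade 2, which Appendix 1 places above 2.5 x ULN, whereas the cholestasis limit is 2 x ULN. Repeat confirmation and exclusion of other causes need clinical judgement. An added row would therefore still not reconcile exactly with the reported serious adverse events.

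A reader might infer that patients commonly qualify on their entry values. The criteria do not support this: Gilbert's syndrome and liver metastases are both needed in one patient, and either alone meets only one limit (profiles D and E). A reader might also infer that the ALP condition excludes nobody. Profile G shows otherwise: it excludes patients whose ALP never falls below 2 x ULN.

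**Conclusion.** The point holds as a statement about the rule. The count labelled Hy's Law is not the protocol's potential liver-injury definition, and it can err in both directions. It can over-count through peaks at different visits, cholestatic events offset by a low ALP elsewhere, and unchanged Gilbert's bilirubin with a new ALT rise. It can under-count in bone-metastatic patients with persistently high total ALP.

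The documents contain no laboratory results, so they do not show that any patient was misclassified, that the net error favours or disfavours ribociclib, or how large it is. The chance-pairing range rests on assumed rates and independence. Cases qualifying wholly on entry values are probably rare, below one patient on the assumed ranges. The change is worthwhile because the table concerns a recognised risk and individual cases matter, not because a material distortion has been demonstrated.

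**What to change.** 1. Keep the existing row in SAP 3.7.2, labelled as a non-concurrent screening count.
2. Add a row that requires the ALT/AST and bilirubin criteria in the same sample, or within a short window stated in the SAP. Apply the protocol 6.5.1.2.1 baseline-dependent limits. Judge cholestasis from ALP and R value at that event. In patients with bone metastases, use the ALP liver fraction where it was measured and flag those without it.
3. State whether the bilirubin limit in the new row is at least 2 x ULN (SAP) or above 2 x ULN (protocol).
4. List every patient in either row with baseline values and ALT, AST, bilirubin and ALP over time. Include cross-over patients, using the cross-over baseline in SAP 2.1.7.
5. If the tables under SAP 3.9.2 are re-issued, treat them in the same way.

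ALT, AST, bilirubin and ALP are in one biochemistry panel (Table 7-4), so the cost is programming, one extra row and one listing. No new data collection is needed, but some bone-metastatic patients will stay unresolved for cholestasis. A same-sample rule can miss a case whose peaks fall on different visits, which the retained screening row will show.
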